**14.1.4 Follow-up Material(s)**

CRF	Event Monitoring Phase		
	Every 6 months until Death	Death	New Primary
Patient Status: Survival and Disease Status Follow-Up/Event Monitoring	X	X	
Consent Withdrawal (choose appropriate withdrawal form): Specimen Only, All Follow-Up 	X		
Lost to Follow-Up 	X		
Notice of New Primary 			At each occurrence

1. If a patient is still alive 5 years after registration, no further follow-up is required.
2. Complete only if applicable

**14.3 Labeling**

Each co-sponsor/participant will be responsible for insuring that all materials contain the patient's initials, MCCC registration number, and MCCC protocol number. Patient's name must be removed.

**14.4 Incomplete materials**

Any materials deemed incomplete by the MCCC Operations Office will be considered "not received" and will not be edited or otherwise processed until the missing information is received. A list of the missing documents will be made available to the appropriate co-sponsor/participant.

**14.5 Overdue lists**

A list of overdue materials and forms for study patients will be generated monthly. The listings will be sorted by location and will include the patient study registration number. The appropriate co-sponsor/participant will be responsible to obtain the overdue material.

**14.6 Corrections forms**

If a correction is necessary the QAS will query the co-sponsor/participant. The query will be sent to the appropriate co-sponsor/participant who will make the correction and return the query and documentation of correction back to the QAS.

**14.7 External Monitoring**

External monitoring of participating sites will occur at pre-determined time points. A data monitoring plan will be generated by a contract research organization. This document will be independent of the protocol. This document will be provided to all study sites for their submission to their local scientific review committees and IRBs as their particular requirements dictate.

## 15. REGULATORY CONSIDERATIONS

### 15.1 Protocol Review and Amendments

Information regarding study conduct and progress will be reported to the Institutional Review Board (IRB) per the current institutional standards of each participating center.

Any changes to the protocol will be made in the form of an amendment and must be approved by the IRB of each institution prior to implementation.

The Protocol Chair (or his designee) is responsible for the coordination and development of all protocol amendments, and will disseminate this information to the participating centers.

### 15.2 Informed Consent

The investigator (or his/her designee) will explain to each subject the nature of the study, its purpose, the procedures involved, the expected duration, the potential risks and benefits involved and any discomfort it may entail. Each subject will be informed that participation in the study is voluntary, that s/he may withdraw from the study at any time, and that withdrawal of consent will not affect her subsequent medical treatment or relationship with the treating physician(s) or institution. The informed consent will be given by means of a standard written statement, written in non-technical language, which will be IRB approved. The subject should read and consider the statement before signing and dating it, and will be given a copy of the document. No subject will enter the study or have study-specific procedures done before his/her informed consent has been obtained.

In accordance with the Health Information Portability and Accountability Act (HIPAA), the written informed consent document (or a separate document to be given in conjunction with the consent document) will include a subject authorization to release medical information to the study sponsor and supporting agencies and/or allow these bodies, a regulatory authority, or Institutional Review Board access to subjects' medical information that includes all hospital records relevant to the study, including subjects' medical history.

### 15.3 Ethics and GCP

This study will be carried out in compliance with the protocol and Good Clinical Practice, as described in:

1. ICH Harmonized Tripartite Guidelines for Good Clinical Practice 1996.
2. US 21 Code of Federal Regulations dealing with clinical studies (including parts 50 and 56 concerning informed consent and IRB regulations).
3. Declaration of Helsinki, concerning medical research in humans (Recommendations Guiding Physicians in Biomedical Research Involving Human Subjects, Helsinki 1964, amended Tokyo 1975, Venice 1983, Hong Kong 1989, Somerset West 1996).

The investigator agrees to adhere to the instructions and procedures described in it and thereby to adhere to the principles of Good Clinical Practice that it conforms to.

## 16. MULTI-CENTER GUIDELINES

### 16.1 Study Documentation

Each participating site is responsible for submitting copies of all relevant regulatory documentation to the Coordinating Center. The required documents include, but are not limited to the following: local IRB approvals (i.e., protocol, consent form, amendments, patient brochures and recruitment material, etc.), IRB membership rosters, summary of unanticipated problems or protocol deviations, and documentation of expertise of the investigators. The Coordinating Center will provide each participating site with a comprehensive list of the necessary documents. It is the responsibility of the participating sites to maintain copies of all documentation submitted to the Coordinating Center.

### 16.2 Records Retention

Following closure of the study, each participating center will maintain a copy of all site study records in a safe and secure location.

### 16.3 Publication

It is understood that any manuscript or releases resulting from the collaborative research will be circulated to all participating sites prior to submission for publication or presentation.

## 17. STATISTICAL CONSIDERATIONS AND METHODOLOGY

The aims of this clinical trial include assessing the impact of adding fulvestrant to alisertib in terms of clinical benefit (response rate and progression-free survival) and safety.

Among the patients who are assigned to alisertib monotherapy (Arm 1) who progress and choose to receive the combination of fulvestrant and alisertib, the primary aims are to examine response and the differences in time to progression with alisertib and that with fulvestrant and alisertib.

Initial treatment refers to alisertib alone for those randomized to Arm 1 and alisertib with fulvestrant for those randomized to Arm 2. Crossover treatment only applies to patients who progress during treatment with alisertib alone on Arm 1.

### 17.1 Assessing the impact of adding fulvestrant to alisertib

#### 17.1.1 Primary Endpoint

The primary endpoint is tumor response rate with initial treatment. That is,

- Arm 1: Tumor response rate is defined as 100% times the number of patients who meet the criteria for CR or PR (using RECIST criteria version 1.1) on 2 consecutive evaluations approximately 8 weeks apart during treatment with alisertib monotherapy divided by the number of patients who started alisertib monotherapy.
- Arm 2: Tumor response rate is defined as 100% times the number of patients who meet the criteria for CR or PR (using RECIST criteria version 1.1) on 2 consecutive evaluations approximately 8 weeks apart

during treatment with combination of alisertib and fulvestrant divided by the number of patients who started treatment with the combination of alisertib and fulvestrant.

The study will test the hypothesis that the addition of fulvestrant to alisertib will increase the tumor response rate over that of alisertib alone by at least 20%.

### 17.1.2 Secondary Endpoints

- 17.1.2.1 Duration of response during initial treatment- time from randomization to disease progression among those patients whose disease meets the RECIST criteria for CR or PR on 2 consecutive evaluations approximately 8 weeks apart during initial treatment.
- 17.1.2.2 Clinical Benefit Rate (CBR) during initial treatment - the proportion of patients who have completed 6 cycles of treatment without disease progression (that is, their objective disease status is a CR, PR, or stable for 6 cycles or more) during initial treatment.
- 17.1.2.3 Progression-free survival (PFS) - time from randomization to disease progression or death due to any cause. If a patient has not had a disease evaluation within 3 months of death, the patient will be censored at the time of last disease evaluation for estimating the distribution of PFS time.
- 17.1.2.4 Safety Profile: The CTCAE version 4.0 will be used to grade and assign attribution to each adverse event reported during initial treatment and crossover treatment separately.

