### 5.2.3 All Institutions

5.2.3.1 Documentation of IRB approval must be on file in the [REDACTED] before an investigator may register any patients.

In addition to submitting initial IRB approval documents, ongoing IRB approval documentation must be on file (no less than annually) at the [REDACTED]. If the necessary documentation is not submitted in advance of attempting patient registration, the registration will not be accepted and the patient may not be enrolled in the protocol until the situation is resolved.

When the study has been permanently closed to patient enrollment, submission of annual IRB approvals to the Registration Office is no longer necessary.

5.2.3.2 Prior to accepting the registration, registration/randomization application will verify the following:

- IRB approval at the registering institution
- Patient eligibility
- Existence of a signed consent form
- Existence of a signed authorization for use and disclosure of protected health information

5.2.3.3 At the time of registration, the following will be recorded:

- Patient has/has not given permission to store and use his/her sample(s) for future research of cancer.
- Patient has/has not given permission to store and use his/her sample(s) for future research to learn, prevent, or treat other health problems.
- Patient has/has not given permission for someone to contact them about future participation in more research
- Patient has/has/not given permission to have coded genetic information and coded medical information placed in password protected, secured database for research analyses.

5.2.3.4 Treatment on this protocol must commence at a TBCRC institution under the supervision of a medical oncologist.

5.2.3.5 Treatment cannot begin prior to randomization and must begin  $\leq 7$  days after randomization.

5.2.3.6 Pretreatment tests/procedures (see Section 11) must be completed within the guidelines specified on the test schedule. Prior to registration/randomization a research biopsy of metastatic breast tissue must be taken for central pathologic review.

5.2.3.7 All required baseline symptoms must be documented and graded.

5.2.3.8 Study drug is available on site.

5.2.3.9 Blood draw kit is available on site.

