## 11. STUDY CALENDAR

### 11.1 Test Schedule for Arm 1: Alisertib

		Pre-registration period (spans the first 28 days after pre-registration) 	Alisertib Treatment Phase		For patients who meet requirements set out in Section 6.1.2 Alisertib + Fulvestrant Treatment Phase	
			Day 1 of each treatment cycle* 	At PD or discontinuation of alisertib	Day 1 of each treatment cycle 	At PD or discontinuation of alisertib + fulvestrant
Tests and procedures	≤28 days prior to Pre-registration					
History and exam, wt, PS	X		X 	X	X	X
Adverse event assessment		X 	X 	X	X	X
Height	X					
Follicle-stimulating hormone (FSH) level 		X				
Hematology group – Hemoglobin – White blood cell count – Absolute neutrophil count – Platelets		X	X 	X	X 	X

 For crossover registration procedure, see Section 5.4

 Hematology and chemistry blood tests and adverse event assessment for registration must be done ≤21 days prior to registration

 Labs, scans, tests and observations may be obtained ≤4 days prior to Day 1 of each cycle.

 Labs, H&E, wt, PS and AE assessment completed prior to switch to the combination of fulvestrant and alisertib may be used for Day 1 of “new” Cycle 1 tests if obtained ≤14 days prior to start of combination treatment.

 For Cycle 1, Day 1, nurse assessment may replace “History and exam, wt and PS” IF most recent physician/provider exam is ≤14 days prior to C1D1.

 Baseline AE assessment is to be performed anytime in the window of ≤4 days prior to registration. AE assessment need not be repeated Cycle 1 Day 1.

 For women <60 years of age with amenorrhea for >12 months

 Hematologic parameters will be assessed on Cycle 1 Day 15 (±1 day) after the patient has taken their morning dose of alisertib

 Hematologic parameters will be assessed on Day 15 (±1 day) of first cycle in the crossover phase any time after the patient has taken their morning dose of alisertib prior to the administration of the loading dose of fulvestrant.

		Pre-registration period (spans the first 28 days after pre-registration) 	Alisertib Treatment Phase		For patients who meet requirements set out in Section 6.1.2  Alisertib + Fulvestrant Treatment Phase	

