			Day 1 of each treatment cycle* 	At PD or discontinuation of alisertib	Day 1 of each treatment cycle 	At PD or discontinuation of alisertib + fulvestrant
Tests and procedures	≤28 days prior to Pre-registration					
Chemistry group – Sodium – Potassium – BUN – Creatinine – Calcium – Glucose – Albumin – AST – ALT  – Alkaline Phosphatase – Total Bilirubin 		X	X	X	X	X
Tumor measurement 	X		X	X	X 	X
Alisertib			X		X	
Fulvestrant					X 	
Patient Medication Diary (Appendix III) 			X	X	X	X

 FOR CYCLE 1 DAY 1 ONLY: If either to the following holds: (1) total bilirubin >1.5 x ULN or (2) Alanine transaminase >5 x ULN, then the patient should not begin protocol treatment. The patient should go off study and will be considered a cancel (see Section 6.4.8).

 The same imaging modality (CT scan, CT component of a PET/CT, or MRI) must be used throughout the study. Baseline imaging should be obtained ≤28 days prior to Registration. Tumor measurements are to be done at the completion of Cycles 2, 4, 6, etc., for first two years or until disease progression, whichever is first. Patients who have achieved complete response, partial response, or stable disease for ≥2 years may reduce imaging to every fourth cycle.

 Scans are not required Day 1 of Cycle 1 of fulvestrant and alisertib. The scans taken at the time of progression on alisertib will serve as the baseline scan for the fulvestrant and alisertib treatment phase of the study.

 Fulvestrant will be given on Day 1 of every cycle and on Day 15 (±1 day) of Cycle 1 only.

 The diary must begin the day the patient starts taking the medication and must be completed per protocol and returned to the treating institution at the completion of each cycle of treatment (approximately every 28 days). Compliance must be documented in the medical record by any member of the care team.

			Alisertib Treatment Phase		For patients who meet requirements set out in Section 6.1.2 Alisertib + Fulvestrant Treatment Phase	
Tests and procedures	≤28 days prior to Pre-registration	Pre-registration period (spans the first 28 days after pre-registration) 	Day 1 of each treatment cycle* 	At PD or discontinuation of alisertib	Day 1 of each treatment cycle 	At PD or discontinuation of alisertib + fulvestrant

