Mandatory tumor tissue specimens for research (see Section 9.0)		X 	X 	X 	X	X 
Research Correlative blood studies (collection for CTCs and cf-DNA)		X	X 	X	X 	X

\* Cycle length is 28 days ±3 days

 The pre-registration biopsy will be utilized for central ER evaluation and correlative studies.

 Performed once up to 4 days prior to the start of Cycle 2. Must be performed prior to initiation of treatment for Cycle 2.

 Performed once up to 14 days after progressive disease is identified. Must be performed prior to initiation of next therapy, which may be the combination of fulvestrant and alisertib for those eligible and electing to crossover, or may be standard therapy for those who elect to come off study or are not eligible for cross-over. If a lung lesion is the only site of disease amenable to a biopsy, then this biopsy will not be mandatory (except for patients with ER <10% or ER negative on the pre-registration biopsy who are desiring and eligible for cross-over).

 Biopsy at PD after crossover is optional, except for patients with a lung lesion as the only site of disease amenable to biopsy in which case the biopsy at PD after crossover is not allowed.

 At the end of Cycle 1, prior to treatment initiation on Day 1 of Cycle 2 (only). May be drawn with clinical labs ≤4 days prior to C2D1.

 At the end of the first cycle of combination therapy, prior to treatment initiation on Day 1 of the second cycle of combination therapy (only).

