#### 12.3.4 Symptomatic Deterioration

Patients with global deterioration of health status requiring discontinuation of treatment without objective evidence of disease progression at that time, and not either related to study treatment or other medical conditions, should be reported as PD due to “symptomatic deterioration.” Every effort should be made to document the objective progression even after discontinuation of treatment due to symptomatic deterioration. A patient is classified as having PD due to “symptomatic deterioration” if any of the following occur that are not either related to study treatment or other medical conditions:

- Weight loss >10% of body weight.
- Worsening of tumor-related symptoms.
- Decline in performance status of >1 level on ECOG scale.

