## 17.4 Analysis of Secondary Endpoints

17.4.1 For each treatment arm, the distribution of PFS times, overall survival times, and duration of response will be estimated using the Kaplan-Meier method.

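### Duration of response is timed from randomization, so the reported figure is time to progression among responders, and death without recorded progression has no rule

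*Combined protocol and SAP*

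**What the plan says.** Section 17.1.2.1 gives the endpoint as "Duration of response during initial treatment- time from randomization to disease progression among those patients whose disease meets the RECIST criteria" for CR or PR at two consecutive evaluations about 8 weeks apart during initial treatment. The origin is randomization, the population is confirmed responders, and the only event is progression.

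In the same list, PFS (17.1.2.3) is "time from randomization to disease progression or death due to any cause". It has its own rule: a patient with no disease evaluation within 3 months of death is censored at the last one. That rule is written for PFS only.

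Section 17.4.1 says that in each arm "the distribution of PFS times, overall survival times, and duration of response will be estimated using the Kaplan-Meier method". It adds no start point, event or censoring rule for duration of response.

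The nearest text on progression without imaging is Section 12.3.4, which begins "Patients with global deterioration of health status requiring discontinuation of treatment without objective evidence of disease progression at that time" and has such cases reported as PD. It does not cover death. Sections 13.4.2 and 13.5.1.3 treat death as a safety report, not as an endpoint event.

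**The concern.** Duration of response should measure how long a response lasts once it exists. Timed from randomization, it becomes time to progression in a subgroup chosen for having responded, and the wait for response is counted as time in response. Every value moves upward.

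There are three consequences:

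- The figure reported under this name is longer than the time patients spent in response, and it cannot be compared with durations timed from first response.
- If patients in one arm respond later than those in the other, the two per-arm estimates shift by different amounts, even when responses last equally long.
- A responder who dies with no PD of either kind (objective or symptomatic) has no event, and the plan does not say whether or when she is censored. This can happen: a patient who stops for unacceptable adverse events moves to event monitoring (Section 6.4.4), where status forms are due every 6 months (Section 14.1.4).

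**Working it through.** The plan states no median, precision or power for this endpoint, so there is no figure to reproduce. The check is a reading of the definition plus schedule arithmetic.

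**Inputs**

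- Scan timing, Section 11.1: "Tumor measurements are to be done at the completion of Cycles 2, 4, 6, etc., for first two years". Arm 2 follows the same schedule (Section 11.2).
- Cycle length, Section 11.1: "Cycle length is 28 days ±3 days", that is 25 to 31 days.
- Scan window, Section 11.1: "Labs, scans, tests and observations may be obtained" up to 4 days before Day 1 of a cycle.
- Start of treatment, Section 5.2.3.5: "Treatment cannot begin prior to randomization and must begin" within 7 days after it, so 0 to 7 days.

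**Days from randomization to scan, with no treatment delay**

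| | Earliest | Nominal | Latest |
|---|---|---|---|
| First scan | 2 × 25 − 4 = 46 | 2 × 28 = 56 | 7 + 2 × 31 = 69 |
| Second scan | 4 × 25 − 4 = 96 | 4 × 28 = 112 | 7 + 4 × 31 = 131 |

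In weeks, the first scan falls at 6.6, 8.0 or 9.9. The 8-week figure is therefore nominal, not a minimum.

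**Relative overstatement** = offset ÷ true time in response, d. The documents do not give d; 20, 28 and 36 weeks are assumed.

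| Offset | d = 20 wk | d = 28 wk | d = 36 wk |
|---|---|---|---|
| 46 days | 33% | 23% | 18% |
| 56 days | 40% | 29% | 22% |
| 69 days | 49% | 35% | 27% |
| 112 days (second scan) | 80% | 57% | 44% |

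**A second anchor.** Assume that responders' median from randomization to progression is 7.9, 12 or 16 months. The first value is the median PFS that Section 17.2 cites for all hormone receptor positive patients in the earlier single-agent study, and it is probably low for responders. At 30.4375 days per month these are 34.4, 52.2 and 69.6 weeks. Subtracting 8 weeks leaves 26.4, 44.2 and 61.6 weeks in response. The overstatement is 8/26.4 = 30%, 8/44.2 = 18% and 8/61.6 = 13%.

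**Responders at different scans.** The tables apply one offset to everyone. A simulation relaxed this, with assumed exponential time to progression after confirmation (medians of 4 to 12 months) and first responses at 8, 16 or 24 weeks. The median was overstated by:

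- 1.8 months if all respond at 8 weeks;
- about 2.6 to 2.7 months with a 70/20/10% split;
- about 3.2 to 3.3 months with a 50/30/20% split.

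Two arms with the same true median of 7.9 months from response would report 10.2 and 11.4 months if first responses split 80/15/5% in one and 40/35/25% in the other. That difference comes only from time to response.

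**Number of responders.** At the design rates, 0.20 × 45 = 9 and 0.40 × 45 = 18, so a few unhandled deaths could move an estimate.

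**The case against.** The definition is explicit and can be estimated: origin, population and event stand in one sentence that nothing else contradicts. On that view the first defect is one of naming. The endpoint also ranks low. It is in none of the Section 2 objectives, has no hypothesis or power statement, and is not tested between arms. The protocol quotes no historical duration of response to compare it with, and gives no sign that time to response will differ by arm; both arms are scanned on the same schedule. The percentages rest on assumed durations, and the largest needs the shortest duration combined with response at the second scan. On death, an analyst would ordinarily censor such a patient, and Section 12.3.4 already narrows the gap.

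Most of this stands as a limit on weight. The plan-based statement is the offset in days; the percentages only illustrate it. The death point alone would be little more than missing detail. But a clear definition does not make the label accurate: followed exactly, it yields a figure that is too long for its name, and a descriptive endpoint is useful only if its number means what the name says.

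A further objection concerns the remedy. Borrowing the PFS censoring rule brings in its 3-month limit, while patients with response or stable disease for 2 years or more may be imaged every fourth cycle: 4 × 28 = 112 days, longer than 3 months (about 91 days). A death late in that interval would be censored because of the schedule alone. This is correct, but the tension lies in the existing PFS rule, affects only those long-term patients, and does not bear on where the clock should start.

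**Conclusion.** The concern holds on both parts. As written, the endpoint is time to progression among confirmed responders and includes each patient's time to response: 46 to 69 days at an undelayed first scan, nominally 56, and nominally 112 at the second. These figures follow from the protocol alone. As a share of true duration, the nominal first-scan offset is 22% to 40% for assumed durations of 36 down to 20 weeks, or 13% to 30% on the anchors timed from randomization. The direction is always upward.

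Death without recorded progression has no rule for this endpoint; the documents do not allow its frequency to be estimated. The consequence is confined to a secondary, descriptive estimate. It should be corrected, but it does not threaten the main conclusions of the trial.

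**What to change.** In Section 17.1.2.1, define duration of response as running from the first evaluation showing a CR or PR that is later confirmed, to progression or death from any cause. State the censoring rule in line with PFS, and set its time limit with the fourth-cycle imaging allowance in mind. Report time to response separately.

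If the randomization-based quantity is wanted, rename it time to progression among responders and state how death without progression is handled. Section 17 already uses time to progression for the crossover patients.

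The cost is a short text change. No extra assessments are needed: RECIST measurement and patient status forms are already scheduled (Section 14.1). That they hold the required dates is inferred from their titles and should be confirmed. Under the first option, reported durations become shorter. Because confirmation is still required, a floor of about 8 weeks from first response remains, compared with about 16 weeks from randomization under the present definition. The rename with a death rule is the cheaper option.
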